## A Introduction

### A1 Study Abstract

Excessive weight gain among young adult women age 18-45 years is an alarming and overlooked trend that must be addressed to reverse the epidemics of obesity and chronic disease. During this vulnerable period women tend to gain disproportionately large amounts of weight compared to men and other life periods. Our team developed a lifestyle modification intervention Healthy Eating & Active Living Taught at Home (HEALTH) that prevented weight gain, promoted sustained weight loss, and reduced waist circumference in an effectiveness trial in partnership with Parents as Teachers (PAT), a national home visiting, community based organization with significant reach in this population. PAT provides parent-child education and services free-of-charge to nearly 170,000 families through up to 25 free home visits per year until the child enters kindergarten. This study will extend our previous work to evaluate dissemination and implementation of HEALTH across three levels (mother, parent educator, PAT site) to achieve widespread impact. We will conduct a pragmatic cluster randomized controlled trial to evaluate HEALTH and the HEALTH training curriculum (implementation strategy) on weight among mothers with overweight and obesity across the US (N= 200 HEALTH; N= 200 usual care). Parent educators from 40 existing PAT sites (20 HEALTH, 20 usual care) will receive the HEALTH training curriculum through the PAT National Center, using PAT's existing training infrastructure, as a continuing education opportunity. An extensive evaluation, guided by RE-AIM, will determine implementation outcomes (acceptability, adoption, appropriateness, feasibility, fidelity, and adaptation) at the parent educator level. The Conceptual Framework for Implementation Research will characterize determinants that influence HEALTH dissemination and implementation at three levels (mother, parent educator, PAT site) to enhance external validity (reach and maintenance) and population level impact. The findings from this innovative study will have significant potential to help reverse the trend of excessive weight gain among young adult women, a critical priority target in battling the epidemics of obesity and chronic disease, by reaching women with an evidence-based intervention nation-wide.

## B Primary Hypothesis

The magnitude of the between-group difference in baseline to 24-month change in weight will be at least 4.7 kg, with mothers receiving HEALTH gaining less weight than those receiving usual care.

## C Background

## D Prior Literature and Studies

Among women, early adulthood (18-45 years of age) is a particularly vulnerable time period, during which they tend to gain disproportionately large amounts of weight,

---

making prevention of weight gain an important target for obesity prevention efforts. Maternal weight change in young adulthood, often initiated during pregnancy and maintained after the postpartum period, can impact obesity risk for the rest of a woman's life. Data from the most recent NHANES survey show that among adult women, the prevalence of obesity in 2011-4 ranged from 12% for Non-Hispanic Asian women to 57% among Non-Hispanic Black women, indicating the burden of obesity is borne disproportionately by some groups. NHANES data also demonstrated that obesity increased among women from 2005-6 to 2013-4, but not among men. Secular trends toward dramatic gains, particularly in young adult women, have been observed in the few representative longitudinal studies that have been conducted. For example, The Coronary Artery Risk Development in Young Adults (CARDIA) study enrolled young adults (18-30 years old) in 1985-6; periodic measurements through 1995-6 found 68% of white women and 78% of Black women who began the study overweight gained at least 5 kg over 10 years and 20% and 29% of these respective groups gained excessive (>20 kg) amounts of weight. Reaching young mothers with interventions that can reverse the trend of excessive weight gain among young adult women is critical to battling the epidemics of obesity and chronic disease.

Dissemination and implementation (D&I) evidence-based interventions, which translate the Diabetes Prevention Program (DPP) into real-world practice, hold promise for impacting the secular trends described above, as prevention of weight gain is a priority intervention target. Follow-up data from the DPP demonstrated the lifestyle intervention, targeting improved dietary intake and physical activity, decreased the incidence of diabetes by 27% over 15 years in overweight and obese adults with impaired glucose tolerance, compared to the placebo group. Moderate weight loss can delay or decrease the risk of developing obesity related diseases, such as cardiovascular disease and diabetes, and metabolic studies have found that for some outcomes, most of the improvement from a weight loss of up to 15%, come with the first 5% of weight lost. Improvement in blood pressure can be achieved even with as little as 3% weight loss. In DPP translation studies, Aziz et al. found the percentage of participants achieving a 5% weight loss ranged from 20% to 64% across interventions. While interventions are able to achieve weight loss, they often ultimately result in diminished effect and weight regain over time. One study found changes in chronic disease risk factors were not different between participants who lost, then regained weight compared to those who did not lose weight.

Despite efforts to translate the DPP to broader populations, evidence-based interventions often fail to reach young women, who are at high risk for weight gain. Women with young children face time and childcare barriers, which impact participation, engagement, and retention; this is of concern as success in programs such as the DPP is associated with attendance. Discrepancies exist between evidence-based, efficacious interventions such as the DPP, and the practical reality of what can be implemented in real-world settings. This study will build on our previous work embedding core DPP elements into the usual practice of a home visiting program that already offers intensive contact over time, and extends this by using PAT's own staff and training infrastructure. This study will also assess the effectiveness of the HEALTH training curriculum (the implementation strategy) and the external validity of this approach when HEALTH is implemented in real-world sites, critical to ensuring sustained impact.

---

## **D1 Rationale for this Study**

Excessive weight gain among young adult women (18-45 years) is an alarming and overlooked trend that must be addressed to reverse the epidemics of obesity and chronic disease. On average, young women gain as much as 0.96 kg per year, for a total of 11.9 kg over 10 years. Based on large scale epidemiologic studies, gaining as little as 2.5 to 10 kg can increase a woman's risk of death from cardiovascular disease by 25%. Development of obesity during childbearing years may also lead to its intergenerational transfer, heightening the need for interventions to prevent weight gain. During this vulnerable period women tend to gain disproportionately large amounts of weight compared to men and other life periods. Evidence-based interventions, such as the DPP, often fail to reach this population due to time and priority constraints. Our team developed an intervention that prevented weight gain and promoted sustained weight loss in partnership with Parents as Teachers (PAT), a national home visiting, community based organization with significant reach in this population. PAT provides parent-child education free-of-charge to women and families, through up to 24 home visits per year that begin prenatally and continue until kindergarten. In 2016, 4,999 parent educators, in 3,246 sites across all 50 states, conducted >1.7 million home visits with nearly 170,000 families.

D&I of an evidence-based intervention within PAT can prevent chronic diseases such as cardiovascular disease and diabetes among mothers nationwide. Since HEALTH is embedded within PAT's existing home visits (without adding visits), which provides long-term interaction with the family (from prenatal until the last child in the home enters kindergarten), it is able to provide a 'limited content + long-term delivery' approach. This approach supports mothers in making incremental changes in eating and physical activity behaviors, and prevents weight gain. In an effectiveness trial, HEALTH led to a 4.7 kg weight difference between groups, reducing weight by 1.5 kg in the intervention group, relative to a 3.2 kg gain in the usual care group over 2 years. Embedding HEALTH within PAT overcomes barriers to participation and reflects the United States Preventive Services Task Force (USPSTF) recommendation of 12 intervention sessions per year. Mothers are already motivated to participate in PAT to benefit their child. This enables participation in HEALTH, an intervention that prevented weight gain, promoted weight loss, and reduced waist circumference (which help prevent cardiovascular disease and diabetes) and is ready for D&I.

The proposed study extends our previous work with a Hybrid Type 2 pragmatic cluster randomized controlled trial to evaluate D&I of HEALTH across three levels (mother, parent educator, PAT site) to achieve widespread impact. First, we will determine weight outcomes among 504 overweight/obese mothers (N=200 HEALTH; N=200 usual care) when parent educators (~8/site) from 40 PAT sites nationwide (20 HEALTH, 20 usual care) receive the HEALTH training curriculum (the implementation strategy) through PAT National Center's existing training infrastructure. From a D&I perspective, an evaluation guided by RE-AIM will measure implementation outcomes (acceptability, appropriateness, feasibility, fidelity, adaptation). Further, the Conceptual Framework for Implementation Research will guide an assessment of factors that influence external validity at multiple levels (mother, parent educator, PAT site) to maximize HEALTH D&I. This innovative study provides the evidence necessary for sustainable D&I of HEALTH across PAT's national network, promoting healthy weight and preventing chronic disease on a national scale.

## **E Study Objectives**

### ***E1 Primary Aim***

**Aim 1. Determine the effectiveness of HEALTH on weight and behaviors among 200 overweight and obese mothers when disseminated and implemented across 20 real-world PAT sites.** We hypothesize:

Hypothesis 1.1 The magnitude of the between-group difference in baseline to 24-month change in weight will be at least 4.7 kg, with mothers receiving HEALTH gaining less weight than those receiving usual care. [primary]

Hypothesis 1.2 Mothers in HEALTH will improve dietary (e.g., reduce sugar beverages) and physical activity (e.g., increase brisk walking) behaviors over 24 months, compared to usual care. [secondary]

Hypothesis 1.3 Relative to usual care, mothers in HEALTH will improve the home food environment. [secondary]

### ***E2 Secondary Aims***

**Aim 2. Evaluate the HEALTH training curriculum's impact on implementation outcomes (e.g., acceptability, fidelity), at the parent educator level, when 112 parent educators (~8/site) are trained by PAT National Center.** We hypothesize that parent educators receiving the HEALTH training curriculum will:

Hypothesis 2.1 Deliver HEALTH with fidelity (adherence, quality of delivery, exposure to the intervention, and participant responsiveness or involvement). [primary]

Hypothesis 2.2 Deliver HEALTH as designed, but adapted for content, consistency, and intensity. [secondary]

Hypothesis 1.3 Rate HEALTH acceptable, appropriate, and feasible to implement in routine practice. [secondary]

**Aim 3. Characterize determinants that influence HEALTH D&I at three levels: mother, parent educator, PAT site to enhance external validity (reach and maintenance/sustainability).**

Question 3.1 Are the mothers participating in HEALTH representative of typical PAT participants?

Question 3.2 What characteristics of parent educators make them more likely to deliver HEALTH with fidelity?

Question 3.3 Are there characteristics of PAT sites that make them more likely to adopt and maintain HEALTH?

### ***E3 Rationale for the Selection of Outcome Measures***

Weight change was selected as the main outcome measure as the aim of the study is prevention of weight gain.

## **F Investigational Agent**

---

## ***F1 Preliminary study***

In the efficacy study (NIDDK grant no. R18DK089461; registered at [www.clinicaltrials.gov](http://www.clinicaltrials.gov) NCT01567033.), women in the usual care versus intervention group were significantly less likely to achieve 5% weight loss at 24 months (11% vs 26%,  $p=0.01$ ). At 12 months, there was a 2.8-kg difference in weight between groups ( $p=0.0006$ ), and by 24 months a 4.7-kg difference in weight (3.2 [SD=7.6] kg vs -1.5 [SD=8.3] kg,  $p=0.002$ ); group differences in waist circumference were also evident by 12 months (2.1 [SD=8.4] cm vs -0.7 [SD=9.8] cm,  $p=0.04$ ) and 24 months (3.8 [SD=10.6] cm vs -2.5 [SD=9.1] cm,  $p=0.005$ ), as were improvements in behavioral outcomes. There was no difference in blood pressure between groups.

## **G Study Design**

### ***G1 Overview or Design Summary***

The study includes a Hybrid Type 2 (efficacy/implementation) cluster randomized trial. Since parent educators from each PAT site will be trained together (risk for contamination) and several research questions relate to the PAT site level, a cluster randomized trial is appropriate. PAT National Center will train educators affiliated with 40 PAT sites in HEALTH; among these, 20 will be randomly assigned to receive the HEALTH training curriculum (implementation strategy), and 20 will serve as controls, delivering usual care PAT. Given the multi-level nature of this study, there are two types of participants: 1) mothers and 2) PAT staff

#### **1.a Inclusion Criteria**

**PAT sites:** Sites will be selected from the pool of 3,246 sites to be among the 40 included in the trial then randomized. To be eligible, sites must report seeing 25 families per year, to assure the required number of mothers per site will be able to be recruited during the study period. Further, to avoid compromising at PAT site's ability to complete its primary function of delivering PAT by imposing the burden of a study, only sites in compliance with the PAT model are eligible.

**Mothers:** As a pragmatic trial, it is important that study participants closely match the usual case load for PAT; inclusion criteria have been selected accordingly. For inclusion in the analytic sample, participants must be 18-45 years of age, overweight or obese (BMI 25-45 kg/m^2), English or Spanish speaking, participating or willing to participate in PAT at a participating PAT site for 2 years, and able to give informed consent for participation.

**PAT staff:** All parent educators at sites participating in the study will be invited to participate. If parent educators elect not to receive the HEALTH training curriculum (the implementation strategy), they will still be allowed to consent to the study and participate in the survey; if they decline to consent to the study and participate in the survey, educators will still be allowed to receive the training; however, mothers on these educators' case loads will not be eligible for the study.

---

### **1.a Exclusion Criteria**

Mothers: Women who are currently pregnant, fewer than 6-months postpartum, or planning to become pregnant in the next 24 months; are unable to speak English or Spanish; and/or are unable to engage in a walking program will be excluded.

PAT staff: at least 18 years of age

### **1.b Participant Recruitment Plans and Consent Process**

Mothers: Our plan to recruit participants mirrors routine PAT ‘rolling’ recruitment throughout the year. Parent educators may provide study fliers or emails to families (parent educators commonly provide materials to families). If the PAT site is hosting an event at which study consent might occur and measures might be taken, parent educators might provide flyers or emails about these events as well. Interested families will either call the number on the flyer or indicate their interest to the parent educator; the parent educator will send the names of mothers who express interest in additional information to the research team who will coordinate an outreach/screening call or text. Screening and data collection procedures will be conducted with a data collector. Data collectors could be a local study team member who calls from (for screening calls) and/or travels from St. Louis (for in person screening and/or measurement) to the site or an individual hired locally to complete data collection. Data collectors will screen potential participants by phone or at site events to ascertain self-reported height and weight, to determine eligibility. If eligible based on self-report, the data collector will consent the participant to a baseline visit and schedule this baseline visit. At the baseline visit, the informed consent process will occur before baseline data collection, with the data collector. These visits may occur in the woman’s home, some other location she prefers (e.g., library, doctor’s office, PAT site), or at PAT site events. As data collection will occur electronically, the participant will have the opportunity to review the consent information on the electronic data collection device (i.e., tablet) before initiating data collection and receive a paper copy of the document, however, we have requested a waiver of documentation of consent. The data collector will also measure height and weight to confirm eligibility based on BMI. Those found to be ineligible and those not providing consent will continue with PAT visits, but will not be part of the study (will not participate in any study measures). To minimize the possibility of coercion or undue influence during the consent process, mothers will have as much time as needed to decide about participation, and the data collector will remind them that their PAT services will not be affected by their decision to participate or not.

PAT staff: When a site agrees to participate in the study, all parent educators will be made aware of the opportunity to participate in the study through a flyer and/or email message and/or announcement at a staff meeting or training. If the parent educator is interested in participating, they will contact the research team by email. Site leaders may also provide a list of educators along with their contact information. The research team will reach out to parent educators by phone and email to conduct informed consent and send the information sheet by email. To minimize the possibility of coercion or undue influence during the consent process, parent educators will have as much time as needed to decide about participation, and the research team will remind them that participating will not affect their employment.

---

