## **J Statistical Plan**

### ***J1 Sample Size Determination and Power***

We are confident the tabulated computations that led to our decision to randomize 40 sites (20 to each arm) are, if anything, conservative. Tabulations are based on weight at 24 months as the primary outcome and are for two-sided tests at the 0.05 significance level.

**Table 2:** Number of subjects required in each PAT site for two-sided tests at the 0.05 level of significance.

# PAT sites per group	Power	Between group difference	Intraclass correlation coefficient		
			0.01	0.02	0.05
19	0.8	4	6	6	7
	0.9	4	8	8	11

---

The table entries (Table 2, above) are the required sample size per cluster completing data collection for power values of .8 and .9; for ICC values of .01, .02, .and .05; for 19 PAT sites per group, and for between group differences of 4 between-group difference in the baseline to 24-month change in body weight that can be detected. Prior data from the HEALTH effectiveness trial found the standard deviation of the change in weight from baseline to 24 months was 8.3 kg. To be conservative, the computations assume an increased value of 10 for the standard deviation. The computations also assume 7 mother will complete 24 months of follow-up at each of 19 PAT sites. The number actually enrolled will be increased to 10 mothers (to account for a potential dropout rate of 30%) and 40 sites (20 per arm). Based on the above parameter assumptions, Table 3 indicates that to achieve a power of 0.8 with 19 PAT sites per group and an intraclass correlation coefficient as high as 0.05, the between-group difference in the change in weight from baseline to 24 months would have to be 4. Since the HEALTH study saw a 24-month decrease in weight of 1.5 (+/- 8.3) kg in the intervention group and a 24-month increase of 3.2 (+/-7.6) kg in the control, we are confident the target of 19 PAT sites per group with 7 mothers providing 24-month data is sufficient. We emphasize these computations are conservative because they allow for more variability (i.e., assume a larger standard deviation) than was observed in HEALTH, and because our analysis will add power by including data on the dropouts who do not provide 24-month data but who do provide data at 12 months.

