### ***L3 Study Timetable***

After initial study set-up (*Table 3*), the collaborative planning phase, IRB approval, and site recruitment and randomization (during August to December 2018), we will begin delivering the HEALTH training curriculum to sites randomized to the HEALTH arm between December 2018 and February 2019. We will begin recruiting mothers in February 2019. With a rolling recruitment, we anticipate recruitment will continue until year 3. This schedule will allow adequate time to finalize analysis, write manuscripts, and disseminate our findings.

Table 3. Study Timeline	Year 1	Year 2	Year 3	Year 4	Year 5
Coordination, collaboration, and planning with PAT National Center	X	X	X	X	X X X X X
Initial site recruitment, data collector training	X				
Parent educators at HEALTH sites receive HEALTH Training Curriculum	X				
Recruitment of families	X	X	X		
Baseline Measurement	X	X	X		
Ongoing HEALTH implementation	X	X	X	X	X
12-month measurement			X X		
24-month measurement				X X X	
Parent educators at Usual Care Sites receive HEALTH Training Curriculum					X
Data analysis, reporting, and dissemination of findings					X X
Sustainability coordination with PAT National Center					X

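### Mothers are recruited after their site is randomised, through educators who know their arm and need not approach everyone, so the weight contrast is open to recruitment bias.

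*Combined protocol and SAP*

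**What the plan says.** **Order of events.** Section L3 (Study Timetable) puts site recruitment and randomisation in August to December 2018 and training of HEALTH-arm educators between December 2018 and February 2019. It then states: "We will begin recruiting mothers in February 2019". Recruitment of mothers is rolling. Section 1.c leaves the randomisation details for later sites to be settled when those sites join.

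**Approach.** Under section 1.b, "Parent educators may provide study fliers or emails to families". A family that is interested either telephones the study or tells the educator. In the second case "the parent educator will send the names of mothers who express interest in additional information to the research team", and that team arranges the outreach call or text. A data collector then screens, obtains consent and confirms BMI.

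**Educator consent.** Under section 1.a, if an educator declines consent to the study, mothers on her "case loads will not be eligible for the study". Section 1.b has educators told of the study once their site agrees to take part. Section H2 places staff consent before HEALTH training. Neither says whether consent comes before or after the site's arm is known.

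**Balance and adjustment.** Section 1.c balances sites on size and percent of low-income families. Section J3 makes covariate adjustment optional, with income as the example. Table 1 in section H2 lists no scale of motivation or readiness to lose weight.

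**The concern.** Cluster randomisation makes the sites comparable. It makes the mothers comparable only if they are identified before allocation, or by a process that cannot respond to it. Here the mothers come in afterwards, and the person who normally puts the flyer in their hands knows the arm. A HEALTH educator has just been trained in a weight programme that she will deliver herself; a usual-care educator has not. Mothers may also respond differently if they learn what their site offers.

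If the share of mothers motivated to lose weight then differs between arms, part of the 24-month weight contrast reflects who was enrolled rather than what HEALTH did. Analysing change from baseline does not remove this, because motivation affects the change itself. Adjusting for income or baseline weight does not remove it either. Enrolling more mothers or sites narrows the confidence interval around a shifted value.

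The documents do not require every potentially eligible mother to be approached, do not require arm-neutral material, and describe no log of mothers approached. A reader of the results could not tell whether recruitment differed between the arms.

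**Working it through.** **1. The plan's own figures, to set the scale.** Section J1 states that its calculations "are for two-sided tests at the 0.05 significance level", "for power values of .8 and .9" and "for 19 PAT sites per group, and for between group differences of 4" (kg). It adds that "the computations assume an increased value of 10 for the standard deviation". The intraclass correlation (ICC) is 0.01, 0.02 or 0.05.

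Effective number per arm = 2 × [SD × (z₀.₉₇₅ + z_power) / difference]²
- Power 0.8: 2 × [10 × (1.960 + 0.842) / 4]² = 98.11
- Power 0.9: 131.34

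Completers per site: m = n × (1 − ICC) / (19 − n × ICC), rounded up.

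| Power | ICC 0.01 | ICC 0.02 | ICC 0.05 |
|---|---|---|---|
| 0.8 | 5.39 → 6 | 5.64 → 6 | 6.61 → 7 |
| 0.9 | 7.35 → 8 | 7.86 → 8 | 10.04 → 11 |

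All six cells of Table 2 are reproduced, and 7 / (1 − 0.3) = 10 enrolled per site. The sample-size arithmetic is not in question.

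**2. Standard error of the contrast.** With 19 sites of 7 completers per arm, SD 10 and ICC 0.05:

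SE = 10 × √[2 × (1 + 6 × 0.05) / (19 × 7)] = 10 × √(2.6 / 133) = 1.40 kg

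**3. Size of a recruitment bias (illustration).** Bias = difference between arms in the share of motivated mothers × extra 24-month weight change in such mothers. Neither input is in the documents; both are assumptions.

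| Case | Share difference | Extra change | Bias | As % of 4 kg |
|---|---|---|---|---|
| Low | 10 points | 2 kg | 0.2 kg | 5% |
| Middle | 20 points | 3 kg | 0.6 kg | 15% |
| High | 30 points | 5 kg | 1.5 kg | 37.5% |

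**4. Effect on the test if HEALTH does nothing.** With the contrast shifted by b, P(reject) = 1 − Φ(1.96 − b/SE) + Φ(−1.96 − b/SE).
- b = 0.2: b/SE = 0.14, P about 5%
- b = 0.6: b/SE = 0.43, P = 0.063 + 0.008, about 7%
- b = 1.5: b/SE = 1.07, P = 0.188 + 0.001, about 19%

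With the earlier trial's SD of 8.3 kg the SE falls to 1.16 kg, and the 1.5 kg case rises to about 25%. A more precise trial is misled more often by the same bias.

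**5. What the existing steps control.**
- Data-collector screening against age and BMI limits controls selection on eligibility, not on motivation.
- Self-referral bypasses the educator for the call, but the flyer or email still normally comes through her.
- Dynamic randomisation acts on two site characteristics, not on the mothers enrolled later.
- Question 3.1 in section E2 compares HEALTH mothers with typical PAT participants, not recruitment between the arms.
- Section K2 gives human-subjects training and study-team status to HEALTH educators. It states no equivalent for usual care, so the two groups of recruiters are not described as working on the same footing.

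**The case against.** The strongest reply is that the educator controls less than it may seem. A reader might infer that she decides whose name goes forward. Section 1.b does not say so: names of mothers who express interest are to be sent, mothers can call directly, emails and site events are further channels, and the research team and data collectors handle outreach, screening and consent. Only the handing out of material is left permissive. That part of the objection stands.

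A reader might also infer that the bias certainly favours HEALTH. The documents do not show this. HEALTH educators might refer the mothers with most difficulty, and usual-care educators recruit for the same weight study, so interested mothers may select themselves there too. The direction is plausible, not established.

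Three further limits are fair:
- Training before recruitment is scheduled for the first HEALTH sites. No training dates are given for later sites, and educators may decline training.
- That the order of educator consent and allocation is unstated is not evidence that consent came afterwards.
- The baseline survey covers diet, activity, home environment and norms, and the instruments are not reproduced. One can say that no motivation measure is listed, not that nothing related is collected.

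Rolling recruitment through PAT is also a deliberate pragmatic choice. It does not depend on an optional approach, though: section 1.a wants participants who match the usual caseload, and approaching everyone serves that better.

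**Conclusion.** The concern holds as a gap in the recruitment procedure. Mothers enter after allocation, through educators who know their arm and are not bound to approach everyone, and nothing planned would reveal a difference between arms in who was approached. That educators know their arm is inferred: the documents describe no blinding, and someone trained to deliver HEALTH cannot be blind to it.

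The size cannot be derived from the documents. On the stated assumptions it runs from 0.2 to 1.5 kg, with 0.6 kg in the middle. The middle value alone would raise the false-positive rate only from 5% to about 7%; the upper value would raise it to about 19%. This does not overturn the design, but it is worth correcting because correction is cheap. Confidence is medium: the sequence and the permissive wording are clear, while direction and size are not.

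**What to change.** 1. In section 1.b, replace the permissive wording with one rule for both arms: every consented educator gives the same arm-neutral flyer to every mother aged 18-45 on her caseload, on a fixed schedule. Outreach by the research team and screening by data collectors stay as they are.
2. Record by site the numbers of mothers on caseload, given a flyer, screened, eligible and enrolled, and report them by arm. The same counts supply a denominator for reach, which Aim 3 needs.
3. For sites not yet allocated, take educator consent, and so fix the eligible caseloads, before the arm is disclosed. This cannot be applied to sites already allocated; items 1 and 2 can still be applied there to remaining recruitment.

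Cost: a procedure edit and one count form per site, with no extra staff or visits, and rolling recruitment is kept. The downside is some additional flyer and counting work for community staff across 40 sites.

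The change reduces differential approach and makes it visible. It does not eliminate the bias, because educators can still promote the study verbally and mothers can still select themselves according to what their site offers.
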